7.1.2 Individual Halting Criteria

Individual Halting Criteria must be reviewed by the site PI prior to administration of the second study vaccination for each subject. It is the responsibility of the site to ensure that any subject meeting the below criteria are discontinued from receiving study product; however, the Emmes BMM or safety monitor may be consulted as needed.

The second study vaccination will not be administered to a subject if any of the following criteria are met, as determined by the site PI:

- Serious adverse event associated with study vaccination.
- Pregnancy in a female subject.
- Type 1 hypersensitivity associated with study product.
- Grade 3 systemic reaction associated with study product.
- Grade 3 local reaction (with the exception of erythema/induration) associated with study product (e.g., pain).
- Grade 2 or higher fever within the first 24 hours following the initial vaccination.
- Medical condition for which continued participation, in the opinion of the site principal investigator or appropriate sub-investigator, would pose a risk to the subject or would be likely to confound interpretation of the results.
- Presence of signs or symptoms that could confound or confuse assessment of study vaccine reactogenicity. For subjects with injection site or systemic signs or symptoms, or with an acute illness, including but not limited to an oral temperature greater than or equal to 100.4°F, the second study vaccination should be postponed/deferred until signs, symptoms, or acute illness have resolved and still within the acceptable protocol-specified window for that visit. If outside this window, the Blinded Medical Monitor must first approve the second study vaccination and the documentation of approval should be filed in the subject's chart.
- Any unresolved or continuing solicited or unsolicited Grade 3 adverse event after first vaccination. An unresolved or continuing Grade 1 or Grade 2 adverse event is permissible unless, in the opinion of the site principal investigator or appropriate subinvestigator, it would render study vaccination unsafe or interfere with the evaluation of responses.
- Grade 2 or higher clinical safety laboratory result that does not decrease to Grade 1 or below prior to the second study vaccination. For a subject to receive the second study vaccination, the most recently evaluated clinical safety laboratory values obtained prior to the second study vaccination must be Grade 1 or less. The

second study vaccination should be scheduled to occur within the acceptable protocol-specified window for that visit. If outside this window, the Blinded Medical Monitor must first approve the second study vaccination and the documentation of approval should be filed in the subject's chart.

- Grade 3 adverse event that occurs without alternative etiology in the 7 days following the first study vaccination.
- Severe or sustained reaction or disability related to the first study vaccination.
- New information becomes available that makes further participation unsafe.

7.2 Participant Withdrawal from the Study and Replacement

7.2.1 Participant Withdrawal

Subjects may voluntarily withdraw their consent for trial participation at any time and for any reason, without penalty or loss of benefits to which they are otherwise entitled.

The site PI or appropriate sub-investigator may also withdraw a subject from receiving the study vaccine for any reason.

A subject may withdraw or be withdrawn from the study for the following reasons:

- Medical disease or condition, or any new clinical finding for which continued participation, in the opinion of the site PI or appropriate sub-investigator, would compromise the safety of the subject, or would interfere with the subject's successful completion of this trial, or would interfere with the evaluation of responses (for example, has baseline significant laboratory abnormalities).
- The subject withdraws consent.
- Subject no longer meets eligibility criteria (see Sections [5.1](#) and [5.2](#)). Note: Medication changes in the 60 days prior to enrollment, as specified in Subject Inclusion Criterion (See Section [5.1](#), Point Number [5](#)), are exclusionary for receipt of the first study vaccination only.
- As deemed necessary by the site PI or appropriate sub-investigator for noncompliance or other reasons.
- The subject is lost to follow-up.
- The study is terminated.
- Any reason that, in the opinion of the investigator, precludes the subject's participation in the study.
- New information becomes available that makes further participation unsafe.

7.2.2 Subject Replacement

Subjects who withdraw, or are withdrawn or terminated from the study, or are lost to follow-up after signing the informed consent form, randomization, and receipt of study vaccine will not be replaced. Subjects who withdraw, or are withdrawn or terminated from the study, or are lost to follow-up after signing the informed consent form and randomization but before receipt of study vaccine may be replaced.

7.3 Lost to Follow-Up

A participant will be considered lost to follow-up if he or she fails to return for scheduled visits and is unable to be contacted by the study site staff.

7.4 Follow up for subjects that discontinued study intervention

The primary reason for withdrawal from this trial will be recorded on the Study Status data collection form (DCF). Subjects will be encouraged to complete the Early Termination Visit. The Early Termination Visit procedures are listed in Section [1.2](#).

Although subjects are free to withdraw at any time or may be withdrawn by the site PI or appropriate sub-investigator at any time (see Section [7.2.1](#)), those subjects who receive only one dose of study vaccine will be encouraged to remain in this trial for follow-up safety assessments (may be conducted by phone call rather than in person) continuing through approximately 6 months after their last study vaccination. These subjects will also be encouraged to provide a venous blood sample for serological assays after their last study vaccination. See the protocol-specific Manual of Procedures (MOP) for alternate follow-up requirements.

Every attempt will be made to follow all AEs, including solicited injection site and systemic reactions, unsolicited non-serious AEs, SAEs, and NOCMCs ongoing at the time of early withdrawal through resolution as per applicable collection times defined for the specific type of AE.

In the case of subjects who fail to appear for a follow-up safety assessment, extensive effort (i.e., three documented contact attempts via phone calls made on separate occasions and followed by a certified letter) will be made to locate or recall them, or at least to determine their health status. These efforts will be documented in the subject's study records.

The site PI or appropriate sub-investigator will inform the subject that already collected data will be retained and analyzed even if the subject withdraws or is withdrawn from this study.

8. STUDY ASSESSMENTS AND PROCEDURES

8.1 Screening and Immunogenicity Assessments

8.1.1 Screening Procedures

Screening procedures may be done up to 28 days prior to enrollment (Day-28 to Day -1). After informed consent the following assessments are performed to determine eligibility and obtain baseline data:

1. Take a focused medical history, including the following information:
 - History of any chronic medical conditions related to inclusion and exclusion criteria.
 - History of any medication allergies including history of hypersensitivity to any components of the study product.
 - Concomitant medications taken within 60 days prior to signing the ICF will be reviewed with subjects to determine stability of chronic diseases and eligibility.
 - Ask if they are participating in another clinical trial or plan to enroll in another clinical trial during the study period.
2. Women of childbearing potentials should be counseled to either practice abstinence or use at least one primary form of contraception from 30 days prior to receipt of study product until 30 days after receipt of the last dose of study vaccine.
3. Sexually active men should be counseled to use contraception from the date of receipt of the first dose of study vaccine until one month after receipt of the second dose of study vaccine.
4. Women of childbearing potential must have a negative serum HCG pregnancy test at screening and a negative urine HCG pregnancy test prior to each dose of study product.
5. Physical exam (standard exam at screening and targeted exam at enrollment).
6. Height and weight measurement (Calculation of Body Mass Index).
7. Vital signs measurement (including HR, BP, oral temperature).
8. Blood for laboratory evaluations.
 - Serology at screening: HIV, Hepatitis B surface antigen, Hepatitis C antibody.
 - Chemistry at screening: sodium, potassium, bicarbonate, calcium, creatinine, glucose [non-fasting], ALT, AST, and total bilirubin.
 - Hematology at screening: white blood cells (WBCs), hemoglobin, and platelet count.
 - Urine for glucose and protein.

Clinical screening laboratory evaluations will be performed locally by the Duke University Health System Clinical Laboratories. Urine pregnancy tests will be performed by trained research staff. The volume of venous blood to be collected is presented in [Table 3](#).

The overall eligibility of the subject to participate in the study will be assessed once all screening values are available. Study subjects who qualify will be randomized into the Advantage eClinical system and all others will be registered as screen failures. Results of screening testing will be discussed with the subject. If a positive result for HIV, hepatitis C or hepatitis B occurs or there is a laboratory result deemed to be clinically significant by the PI, the subject will be referred for appropriate follow-up. Laboratory values that are outside the range of eligibility but are thought to be due to an acute condition or due to laboratory error may be repeated once.

8.1.2 Immunogenicity Assessments

8.1.2.1 Humoral Immunogenicity Tests

Neutralizing YFV-specific antibody responses following vaccination will be assessed by PRNT₅₀ assays performed on blood samples obtained at Baseline (Day 1) and Days 15 and 29 after the first vaccination and at Days 15, 29, 57, and 180 following the second vaccination.

8.1.2.2 Specimen Preparation, Handling, and Shipping

Blood specimens for YFV neutralizing assays will be processed as specified in the MOP and shipped monthly to Fisher BioServices. They will then be sent to OHSU (Beaverton, OR) for testing.

8.2 Safety and Other Assessments

Study procedures are specified in the SoA. A study physician licensed to make medical diagnoses and listed on Form 1572 will be responsible for all trial-related medical decisions.

8.2.1 Physical examination

A targeted physical exam will be performed at baseline and at subsequent in-person visits as indicated by changes in medical history.

8.2.2 Safety Clinical Laboratory Tests

Safety labs will be conducted on blood samples obtained on Days 4 and 15 after each vaccination and on the day of, but prior to, administration of the first and second vaccination (day 29 after first vaccination). Safety labs include hematology tests (hemoglobin, WBC, and platelet count) and blood chemistry tests (sodium, potassium, bicarbonate, calcium, creatinine, glucose [non-fasting], ALT, AST, and total bilirubin).

Urine will be tested by dipstick to evaluate glucose, protein, blood, and leukocyte esterase on days 1, 15 and 29 after first vaccination and day 15 after second vaccination.

Safety labs will be tested locally by Duke University Health System Clinical Laboratories.

For laboratory values outside the site's reference ranges, the site PI will document clinical significance in the eCRF. Any result that is deemed clinically significant but does not meet the protocol's grading criteria ([Appendix A](#)) should either be repeated by the study site, or the subject referred for appropriate clinical follow-up.

For any result that meets the protocol's grading criteria (whether or not it is deemed clinically significant), the PI will also assess relationship to study product, action taken with product, and whether the subject was discontinued due to the event. Graded laboratory abnormalities should be followed until either a return to normal or are judged to be stable, as determined by the PI.

In the absence of a diagnosis, any clinical safety laboratory test result that meets the definition of an SAE as determined by the investigator (e.g., life-threatening) must be reported as an SAE using the AE/SAE form set.

8.2.3 Viremia Detection Tests

Blood samples will be obtained on Day 4 after each vaccination for YFV viremia testing. Viremia testing will include plaque assay and/or RT-PCR. Positive results may be followed by additional testing (e.g., blind passage/amplification). Frozen serum specimens for viremia testing will be shipped to Fisher BioServices. They will then be sent to OHSU (Beaverton, OR) for testing as needed.

8.2.4 Additional Sera Samples

Additional sera samples may be shipped to Fisher BioServices for storage.

8.3 Procedures to be Followed in the Event of Abnormal Laboratory Test Values or Abnormal Clinical Findings

If a physiologic parameter, (e.g., vital signs, or laboratory value) is outside of the protocol-specified range, then the measurement may be repeated once if, in the judgment of the investigator, the abnormality is the result of an acute, short-term, rapidly reversible condition (e.g., stress, anxiety, or "white coat syndrome"). A physiologic parameter may also be repeated if there is a technical problem with the measurement caused by malfunctioning, or an inappropriate measuring device (i.e., inappropriate-sized blood pressure cuff).

8.4 Unscheduled Visit

If the investigator deems the reaction warrants further evaluation or intervention, the investigator will give further instructions on the proper course of action, including a return to the clinic for immediate evaluation at an unscheduled visit if appropriate.

8.5 Adverse Events and Serious Adverse Events

8.5.1 Definition of Adverse Events (AE)

Adverse event means any untoward medical occurrence associated with the use of an intervention in humans, whether or not considered intervention-related (21 CFR 312.32 (a)). An AE can therefore be any unfavorable and unintended sign (including an abnormal laboratory finding), symptom, or disease temporally associated with the use of medicinal (investigational) product.

Any medical condition that is present at the time that the subject is screened will be considered as baseline and not reported as an AE. However, if the severity of any pre-existing medical condition increases, it should be recorded as an AE.

Adverse events can be further divided into solicited adverse events and unsolicited adverse events. Solicited adverse events are those for which the study team will specifically query the participant whether they occurred. Unsolicited adverse events are those events that the subject report occurring without being queried about the specific event.

All AEs will be assessed for severity and relationship to study intervention (see Section [8.5.3.2](#)).

All AEs, solicited and unsolicited, will be captured on the appropriate data collection form. Information to be collected for AEs includes event description, date of onset, assessment of severity, relationship to study product and alternate etiology (assessed only by those with the training and authority to make a diagnosis and listed on the FDA Form 1572 as an investigator), date of resolution, seriousness and outcome. AEs occurring during the trial collection and reporting period will be documented appropriately regardless of relationship. In addition, all medically-attended adverse events (MAAEs) (i.e., events for which medical care from a healthcare provider is sought) will be collected through Study Visit 09.

8.5.1.1 Solicited Adverse Events/Reactogenicity

Solicited adverse events are anticipated local and systemic adverse events for which consistent collection of information is desired. This may include:

- Common and expected events according to the available knowledge about the product, or
- Specific events of concern that should be ascertained on every participant.

All subjects will be observed for at least 30 minutes after each vaccination to detect and treat any immediate adverse reactions. Subjects will be provided with a memory aid, digital, oral thermometer, and ruler for recording daily maximum oral temperature and systemic and local AEs beginning with the day of vaccination and continuing for the next 7 days. Subjects will be encouraged to take their temperature around the same time each day and also if they feel feverish, beginning with the day of vaccination. Subjects will be instructed on how to use the memory aid and how to rate any adverse events. The subject will record temperature and the presence and intensity of post vaccination local reactogenicity events, including signs of redness and swelling and symptoms of pain and tenderness. The subjects will measure redness and swelling at the vaccination site with the measuring device provided. Systemic solicited symptoms will include feverishness, fatigue, headache, chills, nausea, new muscle pain (exclusive of the injection sites), aggravated muscle pain (increase of existing pain, exclusive of the injection site), new joint pain, and aggravated joint pain (increase of existing pain). The subjects will measure temperature with the thermometer provided. Subjects will be instructed to notify the study center if they develop any severe reactions and/or fever equal to or exceeding 101.3°F.

Subjects will also be asked to record any medications taken and any emergency room or physician visits (other than routine check-ups). The subject memory aid will be reviewed with the subject at subsequent clinic visits.

After vaccination, antipyretics or analgesics should not be given routinely. Administration of an antipyretic or analgesic is to be recorded in the memory aid and entered into the CRF.

Injection site symptoms (pain or tenderness) and swelling will be graded as indicated in [Table 4](#).

Table 4. Table of injection site symptom grading

Local Reaction	Mild (Grade 1)	Moderate (Grade 2)	Severe (Grade 3)
Pain – experienced without touching the injection site	Subject is aware of pain but it does not interfere with daily activity and no pain medication is taken	Subject is aware of pain; there is interference with daily activity or requires use of non-narcotic pain medication	Subject is aware of pain and it prevents daily activity, or any use of narcotic pain reliever
Tenderness – hurts only when injection site is touched	Mild discomfort to touch	Discomfort with movement	Significant discomfort at rest
Induration/Swelling ¹	Does not interfere with activity	Interferes with activity	Prevents daily activity

¹Will be also measured but size will not be used as halting criteria

Erythema/redness and induration/swelling as analyzed by measurement will be graded as indicated in [Table 5](#).

Table 5. Table of erythema/redness and induration/swelling grading

Parameter	Grade 1	Grade 2	Grade 3
Erythema/Redness ¹	2.5 – 5 cm	5.1 – 10 cm	> 10 cm
Induration/Swelling ¹	2.5 – 5 cm	5.1 – 10 cm	> 10 cm

¹Will not be used as halting criteria

Note: Induration/Swelling should be evaluated and graded using the symptom scale as well as the actual measurement.

Solicited systemic symptoms will be graded by the subject using the scale in [Table 6](#).

Table 6. Table of systemic symptom grading

Systemic (Subjective)	Mild (Grade 1)	Moderate (Grade 2)	Severe (Grade 3)
Feverishness	No interference with activity	Some interference with activity	Significant interference, prevents daily activity
Fatigue	No interference with activity	Some interference with activity	Significant interference, prevents daily activity
Headache	No interference with activity	Some interference with activity	Significant interference, prevents daily activity
Chills	No interference with activity	Some interference with activity	Significant interference, prevents daily activity
Nausea	No interference with activity	Some interference with activity	Significant interference, prevents daily activity

Systemic (Subjective)	Mild (Grade 1)	Moderate (Grade 2)	Severe (Grade 3)
New muscle pain (exclusive of the injection site)	No interference with activity	Some interference with activity	Significant interference, prevents daily activity
Aggravated muscle pain (increase in existing pain, exclusive of the injection site)	No interference with activity	Some interference with activity	Significant interference, prevents daily activity
New joint pain	No interference with activity	Some interference with activity	Significant interference, prevents daily activity
Aggravated joint pain (increase in existing pain)	No interference with activity	Some interference with activity	Significant interference, prevents daily activity

Fever will be graded as shown in [Table 7](#).

Table 7. Table of fever grading

Oral Temperature	Mild (Grade 1)	Moderate (Grade 2)	Severe (Grade 3)
°C	≥ 37.8 and < 38.5	≥ 38.5 and < 39.0	≥ 39.0
°F	≥ 100.0 and < 101.3	≥ 101.3 and < 102.0	≥ 102.0

Any symptoms still present on Day 8 after the second vaccination will continue to be followed by the subject on the memory aid until two days after symptom resolution.

If a subject experiences an AE or an injection site reaction that is still present at the subject’s EOS visit, the subject will be followed until either resolution of the event/reaction or until the event/reaction is stable, as determined by the site PI. Follow-up procedures, evaluations, and outcomes will be recorded on the subject's case report forms.

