7.1 Halting Criteria and Discontinuation of Study Intervention

7.1.1 Study Halting Criteria

Additional enrollment and study interventions/administration of study products in this trial will be halted for SMC review/recommendation if any of the following are reported:

- Any subject experiences ulceration, abscess, or necrosis at the injection site related to study product administration.
- Any subject presents with laryngospasm, bronchospasm, hypotension or anaphylaxis occurring within 24 hours following product administration that is considered related to study product.
- Two or more subjects experience generalized urticaria (defined as occurring at more than two body parts) within 72 hours after administration of study product that is considered related to study product.
- Any subject experiences an SAE after administration of study product and prior to the subject's last visit that is considered related to study product.
- Two or more subjects who received at least one dose of study vaccine to date, cumulative to all study vaccine administrations, across all treatment arms, experience the same Grade 3 (unsolicited AE or safety laboratory), in the same HLT by MedDRA coding, considered related to study product.

This trial will also be halted for SMC review/recommendation if, within 7 days after administration of either study vaccination, any of the following occurs:

- Three or more subjects who received at least one dose of study vaccine to date, cumulative to all study vaccine administrations, across all treatment arms, experience the same severe (Grade 3) study vaccine-related injection site reaction. Erythema and induration (hardness)/edema (swelling) will also be measured in mm but size will not be used as halting criteria.
- Three or more subjects who received at least one dose of study vaccine to date, cumulative to all study vaccine administrations, across all treatment arms, experience the same severe (Grade 3) study vaccine-related subjective systemic reaction, for which the severity (grade) is corroborated by study personnel.
- Three or more subjects who received at least one dose of study vaccine to date, cumulative to all study vaccine administrations, across all treatment arms, experience the same severe (Grade 3) study vaccine-related quantitative systemic reaction.

Grading scales for solicited injection site and systemic (subjective and quantitative) reactions are included in Section [8.5.1.1](#).

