9.4.2 Analysis of Primary Outcome Measures (Safety)

Solicited AEs and laboratory toxicities will be analyzed by taking the most severe response over the follow-up period, dichotomizing into a binary variable (none or mild versus moderate or severe) and using exact confidence intervals to summarize the reactogenicity and toxicity rates. Tabular and graphical summaries of events will be presented for each solicited symptom, by type (local/systemic/toxicity), severity (none or mild, moderate or severe), and time point post-vaccination.

Unsolicited AEs will be coded by the Medical Dictionary for Regulatory Activities (MedDRA) for preferred term and system organ class. The rate and exact 95% confidence intervals of AEs in aggregate, and by MedDRA categories, will be computed. SAEs will be reported by a detailed listing showing the type, MedDRA coding, relevant dates (vaccination and adverse event), severity, relatedness, and outcome for each event. Primary outcome measures include:

- Occurrence of all serious adverse events (SAEs) at any time during the study.
- Occurrence of all Grade 3 unsolicited adverse events (AEs) from first vaccination through day 29 after the second vaccination.
- Occurrence of all Grade 3 laboratory toxicities from first vaccination through day 15 after the second vaccination.
- Occurrence of solicited local AE and reactogenicity signs and symptoms in the 7 days after each vaccination.
- Occurrence of solicited systemic AE and reactogenicity signs and symptoms in the 7 days after each vaccination.
- Occurrence of any AE through day 29 after the second vaccination.

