10.1.6.2 Internal Safety Review Committee (ISRC)

An internal safety review committee (ISRC), consisting of the blinded medical monitor, clinical program manager and the PI may be convened to provide an option for a rapid review of safety data collected through the day 8 visit following dose one administered to the sentinel cohort of the low dose group and the sentinel cohort of the high dose group. If within the sentinel group during the period from first vaccination through the day 8 visit, no individual halting rule was met, and no more than one unique Grade 3 adverse event (i.e., no same adverse event in more than one subject) was observed then the study will continue with administration of the second vaccination to the sentinel group and initiation of enrollment in the expanded dose cohort. The ISRC may be convened to assist with this objective determination. If the criteria above will not be met, or at the request of the PI and/or NTI, the SMC will be convened to review the sentinel safety data. If the SMC is convened for any reason for review of the sentinel data, the ISRC will not be convened for the cohort and the SMC will determine whether administration of the second vaccination to the sentinel cohort and initiation of enrollment in the expanded dose cohort in order for additional study vaccinations is to be given.

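### The Grade 2/Grade 3 fever cut in Table 7 differs between its Celsius and Fahrenheit rows (39.0 °C is 102.2 °F, not 102.0 °F)

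*Protocol*

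**What the plan says.** Table 7 in Protocol Section 8.5.1.1 is the only scale for measured fever, and it is given in both units. Grade 2 is "≥ 38.5 and < 39.0" in Celsius and "≥ 101.3 and < 102.0" in Fahrenheit. Grade 3 is 39.0 °C or above, or 102.0 °F or above. Grade 1 starts at 37.8 °C or 100.0 °F. There is no statement of which unit governs and no conversion or rounding rule. SAP Section 8 refers the reader back to the protocol for grading scales.

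The Grade 3 category is then used in these places:

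- **Study halting (Protocol 7.1.1).** The trial halts for SMC review if three or more subjects "experience the same severe (Grade 3) study vaccine-related quantitative systemic reaction" within 7 days of either vaccination.
- **Dose 2 (Protocol 7.1.2).** A subject is barred by a "Grade 3 systemic reaction associated with study product", or by a "Grade 3 adverse event that occurs without alternative etiology in the 7 days following the first study vaccination". There is a separate bar for "Grade 2 or higher fever within the first 24 hours following the initial vaccination".
- **Sentinel review (Protocol 10.1.6.2).** The study continues after the sentinel data without convening the SMC if "no individual halting rule was met, and no more than one unique Grade 3 adverse event" occurred by the Day 8 visit.
- **Reporting.** The shells of SAP Tables 11-16 tabulate elevated oral temperature by severity, with separate Moderate and Severe rows.

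**The concern.** A dual-unit table should give the same grade whichever unit is read. Here the two lower cuts match and the top one does not, and the top one defines Grade 3. If the site grades a reading in one unit and a program grades it in the other, the same fever can carry two grades.

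Fever is the only quantitative systemic reaction scaled in Section 8.5.1.1, so Table 7 alone defines what counts toward the halting rule for that class. The same cut decides whether a fever arising after the first 24 hours bars dose 2, provided it is judged related or has no other cause within 7 days. Through that individual rule it also decides whether sentinel data go automatically to the SMC.

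**Working it through.** **Inputs.** All limits come from Table 7. The conversion is °F = 1.8 × °C + 32, with inverse °C = (°F − 32) / 1.8.

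**Step 1: convert each Celsius limit and compare it with the stated Fahrenheit limit.**

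| Cut | °C limit | Converted | Stated °F | Agreement |
|---|---|---|---|---|
| Lower limit, Grade 1 | 37.8 | 1.8 × 37.8 + 32 = 100.04 | 100.0 | yes, to 0.1 |
| Lower limit, Grade 2 | 38.5 | 1.8 × 38.5 + 32 = 101.30 | 101.3 | exact |
| Lower limit, Grade 3 | 39.0 | 1.8 × 39.0 + 32 = 102.20 | 102.0 | no, off by 0.2 |

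**Step 2: grade the readings around the top cut on both rows.**

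| Reading °F | In °C | Rounded °C | Fahrenheit row | Celsius row |
|---|---|---|---|---|
| 101.9 | 38.83 | 38.8 | Grade 2 | Grade 2 |
| 102.0 | 38.89 | 38.9 | Grade 3 | Grade 2 |
| 102.1 | 38.94 | 38.9 | Grade 3 | Grade 2 |
| 102.2 | 39.00 | 39.0 | Grade 3 | Grade 3 |

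The conflict runs from 102.0 to below 102.2 °F and survives rounding to 0.1 °C. In the other direction, a Celsius reading of 38.9 (1.8 × 38.9 + 32 = 102.02 °F) is Grade 2 on its own row and Grade 3 on the Fahrenheit row. The only other mismatch over the range checked (99.5 to 102.9 °F) is 100.0 °F, which is 37.78 °C. It disappears on rounding to 37.8.

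**Step 3: size.** The width is 102.2 − 102.0 = 0.2 °F, or 0.2 / 1.8 = 0.11 °C. Assuming a thermometer that displays 0.1 °F, the Celsius row makes nine readings Grade 2 (101.3 to 102.1) and the Fahrenheit row makes seven (101.3 to 101.9). Two of the nine are in dispute.

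**Step 4: what a disputed reading can change.**

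- *Sentinel review.* One sentinel subject is enough. Take a fever in the range, after the first 24 hours and by Day 8, that is related or has no alternative cause. It meets an individual halting rule on the Fahrenheit row, so the SMC must be convened. On the Celsius row it is a Grade 2 fever and triggers nothing automatically.
- *Dose 2.* The same fever in any subject after dose 1, within the 7-day window where that rule applies, bars dose 2 on one row only.
- *Study halting.* Three subjects with related Grade 3 fever are needed, and at least one must lie in the range for the row to matter.
- *Tables 11-16.* One reclassified subject moves a Severe cell by 1/10 = 10 percentage points in a vaccine group, or 1/5 = 20 points in placebo.

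**Step 5: what it cannot change.** The endpoint counting any occurrence is unaffected. So is the Section 9.4.2 analysis "dichotomizing into a binary variable (none or mild versus moderate or severe"), because Grades 2 and 3 fall on the same side. The first-24-hour fever bar starts at Grade 2 and applies on either row.

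**The case against.** The strongest reply is that the trial probably runs in Fahrenheit. The entry limit (100.0 °F), the dose 2 deferral limit (100.4 °F) and the subject's call threshold (101.3 °F) are all given in that unit, and recruitment is around Durham, NC. If every reading is taken and graded in °F, all subjects are treated alike, and on the stricter row. This is fair, but the protocol does not say so. Table 7 presents both rows as equal, and SAP Listing 13 shows vital-sign temperature in °C. Inconsistent grading is possible, though not demonstrated.

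A second reply is that there are backstops. Fevers of 101.3 °F or more are to be reported to the site, the investigator may withhold vaccine for any reason, and the investigator or sponsor may ask for SMC review of sentinel data. These stand, and they mean that only the automatic triggers differ between rows. Automatic triggers exist, however, so that such decisions do not rest on discretion.

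Two narrower points also stand. The shell of SAP Table 10 has placeholder symptom rows, and SAP Section 8.1.1 leaves measured temperature out of its symptom list, so an effect on Table 10 is an inference. The memory aid is not among the documents, so whether it carries fever grades is unknown.

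**Conclusion.** The mismatch is real and exact. Table 7 contains two definitions of Grade 3 fever, 0.2 °F apart, and nothing in either document chooses between them. The range is narrow and the documents give no fever rate, so no claim is made that the conflict is likely to occur or to alter the trial's conclusions. It should still be corrected, because the affected limit is a decision threshold in a first-in-human trial and a single sentinel subject can be enough to change the automatic review path.

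The conclusion rests only on the current Table 7 and the standard unit conversion. The count of two readings in nine also assumes a 0.1 °F display.

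**What to change.** Preferred: change two cells of the Fahrenheit row, so that Grade 2 runs from 101.3 to below 102.2 °F and Grade 3 starts at 102.2 °F. The version 4.0 amendment rationale gives the aim of aligning Fahrenheit values to the Celsius ones, which points this way as evidence of intent. The drawback is that the Fahrenheit Grade 3 trigger becomes 0.2 °F less conservative.

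Alternative, if 102.0 °F was intended: lower the Celsius cut to 38.9 °C (Grade 2 below 38.9, Grade 3 from 38.9). This keeps the stricter trigger. It needs a stated rule to round to 0.1 °C before grading, because 102.0 °F unrounded is 38.89 °C.

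In either case, state which unit governs, and use the same limit in the programs for SAP Tables 11-16, in Table 10 if measured temperature is reported there, and in the memory aid if it carries fever grades. The cost is two table cells, a sentence and a check of the matching limits.
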